## 1. PURPOSE

The purpose of this MOP is to guide the study's conduct and operations. It will help to facilitate consistency in recruitment, screening, enrollment, randomization, intervention procedures and follow-up procedures, data collection methods, data flow, surveys conducted at different time points and quality control procedures. This guide will supplement the study IRB protocol.

### User/audience

- Principal Investigators, Co-Investigators
- Counselor
- Research Assistants (RA)

## 2. PROCEDURES

Description of responsibilities for study personnel as well as the steps and processes to be followed when conducting the study.

### 2.1.1 Pre-launching

- Before launching the study, the study research assistant will:
  - Approach individuals who attend the HIV clinic at GMU and conduct face-to-face interviews to screen them for eligibility.
  - Get notified by physicians at the clinic of potentially eligible/interested participants so that the RA can conduct face-to-face interviews to screen them for eligibility
  - Get trained on conducting follow-up counseling sessions according to the counseling guide
  - Prepare baseline and follow-up surveys in the same format across participants (via computer, WeChat, in-person etc.)
  - Ensure paper data forms are finalized and computer data entry systems are ready for data entry (EpiData) so that computer-generated spreadsheets of data can be generated
  - The RA will prepare self-help manual and NRT gum for every participant
  - Purchase the CO monitor, train users how to use it for biochemical verification of quitting at 12-month follow-up assessment
  - Train the counselor using the counseling guide that is established to conduct counseling sessions. Counselors should be familiar with the content and procedures of the guide to communicate with participants
  - Counselor should be familiar with referral services around the area/online for smoking cessation

### 2.1.2 Study visits

- **Pre-study visit procedures**
  - Prior to conducting study visits, the RA will ensure that appropriate materials are in place to help in the smooth running of the clinical research study activities. The materials needed to begin the trial is listed in Section 2.4. Below are the procedures needed to be done to begin the trial:
    - Train counselors according to the counseling guide to prepare for the counseling sessions

- Prepare the brief screening agreement, baseline survey, 8-week follow-up survey, and 12-week follow-up survey
- Prepare informed consent form (one form for the study participant to keep, one form to be collected by the RA)
- Set up EpiData system and be ready to enter participant data once the screening process starts
- Prepare approximately 110 envelopes for randomization
- Create a storage location to list participants' phone number
- Create a list to keep track of what messages have been sent to each participant
- Create a WeChat account for the study and for sending text messages
- The RA should be accustomed to accessing the WeChat account and sending the messages to each participant
- Print the self-help manual for each participant (110 copies)
- Purchase and prepare NRT gums to give out to participants (gums will be given out 8 week dosage at a time to all participants)
- Familiarize the usage instructions for the NRT gums to explain to participants
- Obtain usage instruction of the NRT gums to hand out to participants
- Training on using the CO monitor and filters (at least 100)
- **Study visit procedures**
  - The RA will conduct face-to-face interviews with potential participants and ask the screening questions (Refer to document 1: brief screening agreement)
    - If eligible: Make a note in tracking system that an individual was screened and was eligible, and the criteria for which they were eligible. Answers will not be retained.
    - If not eligible: Make a note in tracking system that an individual was screened and was ineligible, and note the criteria for which they were ineligible. Answers will not be retained.
  - The RA will collect and verify all signed informed consent documents and place them in participants' study folders (labeled by ID number).
  - Participants will receive a signed copy of the informed consent form
  - The RA will add participants' WeChat contact after participants have signed the informed consent form and are randomized into the intervention group
  - The RA will record participants' phone number for follow-up counseling sessions (Refer to document 11: tracking spreadsheet)
  - Record survey completion status for each participant

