### 2.1.3 Randomization

- Study statistician will produce a randomization scheme that is unknown to the RAs and produce 110 envelopes for randomization. Half of the envelopes indicate that participants are assigned to the control group, half of the envelopes indicate that participants are assigned to the intervention group
- After the completion of baseline questionnaire, RA is going to randomly open up an envelope to assign participants to either the control or the intervention group

- The RA is going to input participants' ID number and their assigned group into the data storage system (EpiData)

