### Step 2: Informed Consent Process

- RA must have enough copies of the consent documentation (Refer to document 2:adult informed consent form)
- The RA will conduct the consent process in a private location, hand out the printed consent form and review the form with the participant
- If the participant provides consent to participate, the adult informed consent form should be maintained in the participant's study file
- A copy of the signed consent document will be provided to the participant to keep
- RA will submit the signed participant informed consent forms to the study coordinator to be saved in the participant study file

Note: If a participant is withdrawn after enrollment, the consent form should still be maintained and not destroyed

- The study team obtaining the consent must also sign and date the consent form
- Record date the ICF has been signed on a tracking spreadsheet (Refer to document 11: tracking spreadsheet)
- The RA will record participant's contact information including WeChat name and telephone number (Refer to document 11: tracking spreadsheet)

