#### **Step 6: Follow-up Visits**

- The RA is going to administer the follow-up survey at 8-week and 12-week (Refer to document 4: 8-week survey and document 5: 12-week survey)
- RA has the flexibility to administer the surveys over WeChat or phone if in-person administration is not possible
- The RA is going to make sure that surveys are completed by the participants and have participants' ID number on each survey
- The RA is going to enter ID numbers and responses into EpiData

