## **2.3 MATERIALS**

1. Brief screen agreement
2. Adult consent form
3. Baseline survey
4. 8-week follow-up survey
5. 12-week follow-up survey
6. Text messages
7. Counseling guide
8. Self-help manual
9. CO monitor
10. 100 filters for the monitor
11. Tracking spreadsheet
  - a. Spreadsheet with enrollment progress (date and ICF)
  - b. Spreadsheet with contact information (WeChat account names, phone numbers)
  - c. Spreadsheet with text message schedule for each participant
  - d. Spreadsheet of NRT gum usage

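### Only intervention participants are added on WeChat, yet WeChat is a fallback route for the follow-up surveys, so survey mode and completeness can differ by arm

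*Combined protocol and SAP*

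**What the plan says.** Four parts of the manual bear on this.

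- **Adding the contact (section 2.1.2).** "The RA will add participants' WeChat contact after participants have signed the informed consent form and are randomized into the intervention group". The same section describes the account more broadly: "Create a WeChat account for the study and for sending text messages". Neither this section nor the control-group step (section 2.2, Research Assistant, Step 5) has a matching instruction for control participants.
- **Recording contact details (Research Assistant, Step 2).** At consent, "The RA will record participant's contact information including WeChat name and telephone number". This is not limited by arm. It comes before allocation, since section 2.1.3 says "After the completion of baseline questionnaire, RA is going to randomly open up an envelope to assign participants".
- **Collecting the surveys (Research Assistant, Step 6).** For the 8- and 12-week surveys, "RA has the flexibility to administer the surveys over WeChat or phone if in-person administration is not possible". This is not limited by arm either.
- **Survey format (section 2.1.1).** The surveys are to be prepared in one format for all participants.

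The primary outcome in section 2.4 is exhaled CO at 12 weeks, split at 8 ppm. The secondary outcomes are 7-day point prevalence abstinence at 8 and 12 weeks, quality of life, ART adherence, change in smoking quantity and quit attempts. Section 2.4 has no rule for missing outcomes.

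**The concern.** Follow-up should be pursued in the same way in both arms. Here the step that opens a WeChat link depends on the allocation, and the same channel may later be used to collect outcomes. An intervention participant who misses a visit can be surveyed through a link that already carries the program messages. A control participant in the same position has a WeChat name on a spreadsheet, but no described step that turns the name into a contact.

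Two things could then differ by arm. One is completeness: more surveys may be recovered in the intervention arm. The other is mode: more intervention surveys may be answered remotely, to the same research assistant and on the same channel that delivered the messages. Both matter for self-reported abstinence, and the 8-week result has no CO measurement to check it against. The manual tracks survey completion but not survey mode or contact attempts, so a difference in mode could go unseen.

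**Working it through.** **Step 1: set the instructions side by side.**

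| Step | Intervention | Control |
|---|---|---|
| WeChat name and phone recorded at consent | Yes | Yes |
| Added on the study WeChat account | Yes, after randomization | Not described |
| In-person survey (default) | Yes | Yes |
| Phone as fallback | Yes | Yes |
| WeChat as fallback | Permitted, link in place | Permitted, no link described |

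The arms differ in one row of procedure, and that row matters only when an in-person survey fails. I assume that a recorded name is less ready to use than an added contact; the manual treats them as separate steps at different times.

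**Step 2: which outcomes are exposed.** A survey over WeChat can supply the self-reported outcomes. It cannot supply exhaled CO, so the primary outcome is exposed only if the channel changes who attends at 12 weeks. The manual describes no WeChat visit reminders.

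**Step 3: illustrate the size.** The plan has no figure to reproduce: it gives no abstinence rate, follow-up rate or missing-data rule. Its only usable number is 110 envelopes, or 110/2 = 55 per arm. Everything else here is assumed: true abstinence p, equal in both arms, and follow-up rI (intervention) and rC (control). Any apparent difference is therefore spurious.

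*Missing counted as smoking.* The apparent rate is p × r in each arm, so the difference is p × (rI − rC). With p = 0.20, rI = 0.90 and rC = 0.80:

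- intervention 0.20 × 0.90 = 18%; control 0.20 × 0.80 = 16%; difference 2 points
- odds ratio (0.18/0.82)/(0.16/0.84) = 0.2195/0.1905 = 1.15
- in participants: 0.02 × 55 = 1.1 per arm of 55

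*Complete cases, missingness unrelated to outcome within arm.* The rate is (p × r)/r = p in both arms, so the difference is 0.

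*Complete cases, extra control loss only among non-quitters.* The control rate is p × rI/rC = 0.20 × 0.90/0.80 = 22.5%, against 20% in the intervention arm: −2.5 points, against the intervention.

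Range over the assumed values (percentage points, intervention minus control):

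| p | Follow-up | Missing = smoking | Complete case, unrelated | Complete case, extra control loss in non-quitters |
|---|---|---|---|---|
| 0.10 | 90% vs 80% | +1 | 0 | −1.25 |
| 0.20 | 90% vs 80% | +2 | 0 | −2.5 |
| 0.30 | 90% vs 80% | +3 | 0 | −3.75 |
| 0.10 | 90% vs 70% | +2 | 0 | −2.9 |
| 0.20 | 90% vs 70% | +4 | 0 | −5.7 |
| 0.30 | 90% vs 70% | +6 | 0 | −8.6 |

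With equal follow-up (90% in both arms) the difference is 0 under all three rules. Nothing in the documents supports a 10- or 20-point gap from this one step. At p = 0.20, each point of gap moves the missing-as-smoking comparison by 0.2 points.

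**The case against.** The strongest reply is that silence is not prohibition. The section 2.1.2 bullet can be read as setting up delivery of the program messages, which only the intervention arm receives. Step 6 offers WeChat or phone without regard to arm, every participant's WeChat name and phone number are on file before allocation, and section 2.1.1 asks for a common format. On that reading, a research assistant could add a control participant when needed. Even if none did, in-person and phone contact remain. The manual also supplements an IRB protocol that is not among the documents here and may contain follow-up contact rules.

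Much of this stands, and it rules out three stronger conclusions that a reader might infer:

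- **That reach does differ by arm.** The text shows only that it can. Phone is an equal alternative to WeChat in Step 6. Section 2.1.2 links phone numbers to counseling, but Step 2 records them for everyone without that limit.
- **That the primary comparison is biased.** CO cannot be collected over WeChat, and no mechanism acting on visit attendance is described.
- **That the bias could not be dealt with in analysis.** Completion can be compared by arm, and sensitivity analyses could bound the effect, though not remove it.

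It is also fair that intervention participants have more contact by design, through messages and four counseling sessions. Equal WeChat access would not remove that.

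What the reply does not remove is the instruction itself. It makes a contact step depend on allocation, and nothing else in the manual restores the balance.

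**Conclusion.** The point holds as a low-priority procedural one. As written, the intervention arm has an extra live fallback channel for the 8- and 12-week surveys, so survey mode and completeness can differ by arm. The exposed outcomes are the self-reported ones; any effect on the primary CO outcome would be indirect.

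The size is unknown and probably small. The illustrative 2-point shift rests on assumed abstinence and follow-up rates and on counting missing as smoking. Under other assumptions the shift is zero or runs against the intervention. Because the plan states no missing-data rule, the direction cannot be fixed in advance.

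**What to change.** Replace the section 2.1.2 bullet with wording to this effect: the research assistant adds every participant's WeChat contact at consent, before the randomization envelope is opened; program messages go to the intervention arm only.

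Add to Step 6 that both arms are followed up through the same channels, in the same order and with the same number of attempts, and that the mode of each completed survey is recorded.

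The cost is a few sentences and one tracking field. WeChat names are already collected from everyone, so no new contact data are needed. The downside is a small risk of sending a program message to a control participant. The per-participant message log already in the plan limits that risk.

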### 2.1.3 Randomization

- Study statistician will produce a randomization scheme that is unknown to the RAs and produce 110 envelopes for randomization. Half of the envelopes indicate that participants are assigned to the control group, half of the envelopes indicate that participants are assigned to the intervention group
- After the completion of baseline questionnaire, RA is going to randomly open up an envelope to assign participants to either the control or the intervention group

- The RA is going to input participants' ID number and their assigned group into the data storage system (EpiData)

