#### 2.1.4 Monitoring

- The principal investigators will periodically monitor the trial progression to ensure aspects of the protocol are followed
- Study and source documentation will be reviewed for verification of data collected. Check the source documentation at visits
- Review the participants' study folders to ensure it is complete and current
- Create a tracking spreadsheet to keep track of participant activities, such as enrollment progress, phone numbers, WeChat account names, text message schedule for each participant, and NRT usage (Refer to document 11: tracking spreadsheet)
- Meeting with the study coordinator approximately once a week to review any issues found during screening, enrollment and any other study activities

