### Step 3: Survey Administration and Randomization

- After participants sign the informed consent document, RA will administer the baseline survey, baseline demographics, smoking habits, and other information will be surveyed (Refer to document 3: baseline survey)
- For accurate baseline measurements, the protocol below will be followed:
  - The RA will conduct face-to-face baseline surveying process to all participants

- After participants complete the baseline survey, RA will make sure participant ID is written on the survey
  - Participant's identifiers are going to be removed from the survey and gets stored in another location separated from the survey answers. Survey responses are going to match participants' ID number in EpiData
  - The RA will enter the participant's ID and responses into EpiData
- The RA is going to conduct the randomization process after baseline surveys are completed. Corresponding participant ID and assigned group should be entered into EpiData

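### The RA chooses which of the 110 envelopes to open and only ID and arm are recorded, so blind drawing could not be verified and a modest departure could not be reliably detected

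*Combined protocol and SAP*

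**What the plan says.** Section 2.1.3 (Randomization) separates preparation from use. The "Study statistician will produce a randomization scheme that is unknown to the RAs and produce 110 envelopes for randomization", with half of the envelopes for each arm. Once the baseline questionnaire is complete, the "RA is going to randomly open up an envelope to assign participants to either the control or the intervention group".

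The role that opens the envelope has already met the participant. Section 2.1.2 has the RA screen face to face, and Step 3 of the Research Assistant section adds: "The RA will conduct face-to-face baseline surveying process to all participants".

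On records, Step 3 says: "Corresponding participant ID and assigned group should be entered into EpiData". Section 2.1.3 asks for the same two items and no others.

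Monitoring is general. Section 2.1.4 states "Study and source documentation will be reviewed for verification of data collected", and adds checks of participant folders and roughly weekly meetings. The four tracking sheets in section 2.3 cover enrollment and consent date, contact details, message schedule and gum use. None is described as holding an envelope number or an opening date.

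Section 1 says of the manual: "This guide will supplement the study IRB protocol". That protocol is not in the file.

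**The concern.** Freedom from selection bias here depends on each draw being blind. The manual leaves the choice of envelope to someone who has just heard the participant's smoking history, and it fixes no sequence that could later be compared with what was done. Suppose an RA opened an envelope, did not want that arm for that person, drew another and put the first back. ID and arm would be entered exactly as after an honest draw.

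At stake is the main comparison, a logistic regression of CO-defined cessation at 12 weeks on treatment group. If the allocation were challenged, the records described could not show that it had been followed.

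**Working it through.** **1. The plan's own figure.** 110 / 2 = 55 envelopes per arm, which is consistent. The documents give no sample-size calculation, alpha or expected quit rate, so everything from step 3 on rests on assumptions.

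**2. What each described record can show.**
- *ID and arm in EpiData:* the same after a blind draw and after a redraw.
- *Arm totals:* if all 110 envelopes are used, the totals are 55/55 whatever the RA does, as they were in every simulated trial. Section 2.1.2 speaks of approximately 110 envelopes and no section fixes enrollment at 110, so this is conditional.
- *Order of arms:* consent dates give an approximate enrollment order. A runs test on arm in that order rejected in about 4% to 5% of simulated trials whether 0% or 30% of assignments were steered, so it carries no signal.
- *Baseline comparisons (section 2.4, item 1):* these can react if the steered trait is among the tested variables; see step 5.

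**3. Assumed inputs (none is in the documents).** No treatment effect; overall quit rate 20%; half of participants have quit rate 20% + d/2 and half 20% − d/2, with d = 10, 20 or 30 points; steering is always better prognosis to intervention and poorer to control; f = 10% or 20%; all 110 envelopes used; two-sided 5% unadjusted z-test.
- *One redraw:* when the drawn arm is unwanted, with probability f the envelope is returned and one other is drawn and kept.
- *Upper case:* the wanted arm is always obtained in a share f of draws while it remains.

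**4. Size of the effect.** A hand approximation comes first. The between-arm difference in the share with better prognosis is 2 × P(wanted arm) − 1, and bias is d times that.
- One redraw: P = 1/2 + (1/2)(f)(1/2) = 1/2 + f/4, so bias ≈ d × f/2. For f = 20%, d = 30: 30 × 0.10 = 3.0 points. Expected redraws ≈ 110 × 1/2 × f = 5.5 or 11.
- Upper case: P = f + (1 − f)/2 = 1/2 + f/2, so bias ≈ d × f. For f = 20%, d = 30: 30 × 0.20 = 6.0 points.

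Simulation from the finite 55/55 set (40,000 trials per cell) gives bias in points / type I error:

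| f | d | One redraw | Upper case |
|---|---|---|---|
| 0 | 10, 20, 30 | 0 / 5.1%, 5.2%, 5.2% | 0 / 4.8%, 5.1%, 5.1% |
| 10% | 10 | 0.4 / 5.3% | 1.0 / 5.6% |
| 10% | 20 | 1.0 / 5.2% | 1.9 / 5.9% |
| 10% | 30 | 1.5 / 5.4% | 2.9 / 6.9% |
| 20% | 10 | 1.1 / 5.1% | 2.0 / 5.9% |
| 20% | 20 | 2.0 / 6.0% | 3.9 / 8.2% |
| 20% | 30 | 3.0 / 6.8% | 5.9 / 12.3% |

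Monte Carlo error of the type I error is about 0.1 to 0.2 points. For scale, the null standard error of the risk difference is sqrt(2 × 0.2 × 0.8 / 55) = 0.076, or 7.6 points. If a quarter of the steering runs the other way (f = 20%), bias falls to 0.5 to 1.5 points (one redraw) or 1.1 to 3.0 points (upper case).

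**5. Would the baseline tests show it?** A 5% test on the steered trait itself, if measured, rejected in about 7% to 17% of trials with one redraw and 17% to 52% in the upper case (f = 10% to 20%), against about 5% with honest draws.

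**6. Effect of adjustment.** This assumes that the steered trait is measured and is adjusted for only when its baseline test is significant, as in section 2.4, item 1, using Mantel-Haenszel stratification with 8,000 trials per cell. In the upper case at f = 20%, type I error fell from 12.6% to 5.9% for d = 30 and from 7.9% to 5.2% for d = 20.

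**The case against.** The strongest reply is that the written procedure is sound. A blind draw from a half-and-half set is random, the RAs do not know the scheme, and consent and the baseline survey both precede opening, so under the written rule enrollment cannot depend on a revealed arm. An unordered set also has no identifiable next envelope to preview. All of this stands. It means that harm requires breaking the rule; it does not supply a record that the rule was kept.

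A reader might infer that a departure could not be detected at all. The documents do not support that. The planned baseline comparisons could give a signal, and step 5 shows that it is not negligible for heavy steering. The signal is still indirect. It needs the trait to be measured and tested, item 1 of section 2.4 names demographic variables and uses the tests to choose covariates, and a significant result cannot be told apart from chance imbalance.

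A redraw might also leave a physical trace, because a returned envelope would already be open unless resealed. That is fair, and the simulation ignores it by treating the returned envelope as an ordinary blind one. However, the manual describes no inspection of unused envelopes and no retention of opened ones.

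The 12% figure could be read as the expected error rate. It is not. It is the extreme corner of the upper case, for the unadjusted analysis, with prognosis groups of 35% and 5% identified without error. Adjustment removes most of the excess when the trait is measured, but an RA's impression of a participant may not be a measured variable.

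Finally, the IRB protocol may contain the missing safeguards. That cannot be checked here.

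**Conclusion.** The point holds as a gap in verifiability. The manual leaves the choice of envelope to the RA and describes no record linking envelope, participant and order. Blind drawing therefore could not be confirmed afterwards, and modest steering could not be reliably detected.

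If every draw is blind there is no bias. Under the assumed inputs, unadjusted bias is about 0.4 to 3 points with type I error of about 5% to 7% in the one-redraw case, and up to about 6 points and 12% in the upper case. In the more plausible range the effect is small beside a 7.6-point standard error, and adjustment on a measured trait reduces it further.

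A reader might go on to infer that the allocation is invalid or that RAs will steer it. Nothing in the documents says so. The case for acting is that the main comparison depends on allocation that can be shown to have been followed, and showing it costs very little.

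**What to change.** Replace the free draw in section 2.1.3, and align Step 3 of the Research Assistant section, with wording such as: *The statistician prepares consecutively numbered, opaque, sealed envelopes from the generated sequence. After the baseline survey the RA writes the participant ID and the date on the lowest-numbered unopened envelope and then opens it. The envelope number is entered in EpiData with the ID and arm. Opened envelopes are kept, and the statistician periodically reconciles used and unused envelopes against the list.*

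If the IRB protocol already says this, the manual should be brought into line with it. Numbering does not make early opening impossible, but it removes the choice of envelope and makes departures visible at reconciliation.

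The cost is a few lines of text, numbers on envelopes that are being made anyway, one more EpiData field and a periodic count. Sample size and analysis do not change. The only downside is a little extra record-keeping.
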